6.6. Concomitant Medications

For participants in the FAS population, concomitant medications will be coded using the WHO Drug Dictionary and summarized as number and percentage of participants with concomitant medications by WHO drug class and WHO drug term.

Concomitant medications will be summarized by treatment groups for each cohort. Also, listings will be provided for both Cohorts A and B.

7. EFFICACY

Appendix A provides a list of planned tables, figures, and listings. Sample data displays are included in a separate document.

7.1. General Considerations

For all continuous variables, both the actual value, change, and percentage from baseline (if available) will be analyzed.

All by-visit analyses will include the follow-up period if the data are available.

7.2. Efficacy Measures

7.2.1. Body Surface Area

Facial and total %BSA (includes facial and nonfacial areas) depigmented by vitiligo will be estimated at each visit. Body surface area assessment will be performed by the palmar method. Body surface area should be estimated to the nearest 0.1%. The approximate size of the participant's entire palmar surface (ie, the palm plus 5 digits) should be considered as 1% BSA, and the approximate size of the participant's thumb should be considered as 0.1% BSA.

7.2.2. Vitiligo Area Scoring Index

Areas affected by depigmentation due to vitiligo will be assessed using the VASI. It is based on a composite estimate of the overall area of vitiligo patches at baseline and the degree of macular repigmentation within these patches over time.

Facial VASI is measured by percentage of vitiligo involvement (%BSA) and the degree of depigmentation. The percentage of BSA (hand unit) vitiligo involvement is estimated by the investigator using the palmar method. Hand unit is based on the participant's hand size. The investigator uses their hand to mimic the participant's hand size to evaluate percentage of BSA vitiligo involvement. The degree of depigmentation for each vitiligo involvement site is determined and estimated to the nearest of the following percentages: 0, 10%, 25%, 50%, 75%, 90%, or 100%. At 100% depigmentation, no pigment is present; at 90%, specks of pigment are present; at 75%, the depigmented area exceeds the pigmented area; at 50%, the depigmented and pigmented area are equal; at 25%, the pigmented area exceeds the depigmented area; at 10%, only specks of depigmentation are present. The F-VASI is then derived by multiplying the values assessed for the vitiligo involvement by the percentage of affected skin for each site on the face and summing the values of all sites together (possible range, 0-3).

[figure not shown]
The area "Face" is defined as including the area on the forehead to the original hairline, on the cheek to the jawline vertically to the jawline and laterally from the corner of the mouth to the tragus. The area "Face" will not include the surface area of the lips, scalp, ears, or neck but will include the nose and eyelids.

Total body VASI is calculated using a formula that includes contributions from all body regions (possible range, 0-100).

$$VASI = \sum_{all\ body\ sites} [hand\ units]\ x\ [Residual\ Depigmentation]$$

The body is divided into the following 6 separate and mutually exclusive sites: 1) head/neck, 2) hands, 3) upper extremities (excluding hands), 4) trunk, 5) lower extremities (excluding feet), and 6) feet. The percentage of vitiligo involvement is estimated in hand units (%BSA) by the same investigator during the entire course of the study. Hand unit is based on the participant's hand size. The investigator uses their hand to mimic the participant's hand size to evaluate %BSA vitiligo involvement. The degree of depigmentation for each body site is determined and estimated to the nearest of the following percentages: 0%, 10%, 25%, 50%, 75%, 90%, or 100%. The T-VASI is then derived by multiplying the values assessed for the vitiligo involvement by the percentage of affected skin for each body site and summing the values of all body sites together (Hamzavi et al 2004).

The categorical variable F-VASI50 will be equal to 1 for percentage improvement from baseline in F-VASI of \geq 50% and will be equal to 0 for percentage improvement of \leq 50%. The F-VASI75/90 and T-VASI75/90 will be defined with the same pattern.

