1. INTRODUCTION

This is a Phase 3, double-blind, vehicle-controlled, randomized withdrawal and treatment extension study that will enroll eligible participants who have completed either Study INCB 18424-306 or Study INCB 18424-307 (parent studies) in which the participants will have been using ruxolitinib cream 1.5% BID for the previous 28 to 52 weeks (depending on their initial randomization in the parent study). Participants who successfully completed either of the parent studies and tolerated ruxolitinib cream treatment without a safety concern and with good compliance for continuation may be eligible to participate in this treatment extension study.

Eligible participants in this treatment extension study will be assigned to 1 of 2 cohorts, Cohort A or Cohort B, based on their F-VASI responses at the time of enrollment in this extension study (ie, at Week 52). Participants who achieved complete or almost complete facial repigmentation (ie, achieved \geq F-VASI90) at Week 52 in the parent study will be assigned to Cohort A, stratified by the original treatment received on study Day 1 of the parent study, and randomized 1:1 to treatment with vehicle cream BID or ruxolitinib cream 1.5% BID for an additional 52 weeks (ie, until EOT or at Week 104). However, any participant in Cohort A who experiences relapse (defined as \leq F-VASI75) will receive ruxolitinib cream 1.5% BID as an open-label rescue treatment until they complete treatment (Week 104 or EOT). Participants who did not achieve \geq F-VASI90 at Week 52 of the parent studies will be assigned to Cohort B and will continue ruxolitinib cream 1.5% BID for up to 52 weeks (ie, EOT or Week 104).

The purpose of this SAP is to provide details of the statistical analyses that have been outlined in the study Protocol. The scope of this plan will be executed by the Department of Biostatistics or designee, and the analyses of PK will be executed by the Department of Clinical Pharmacokinetics or designee.

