7.3. Analysis of the Primary Efficacy Parameter

The primary endpoint is time to relapse (defined as < F-VASI75) for participants who are randomized in Cohort A.

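### SAP 7.2.2 codes an improvement exactly on the 50/75/90% cut-off as both response and non-response, and SAP Section 1 states relapse with a different inequality from the rest of the plan

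*SAP*

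**What the plan says.** **Responder flags.** SAP 7.2.2 gives the rule for a 1: "The categorical variable F-VASI50 will be equal to 1 for percentage improvement from baseline in F-VASI of \geq 50"%. It then gives the rule for a 0 and extends both rules to the other flags: the variable "will be equal to 0 for percentage improvement of \leq 50%. The F-VASI75/90 and T-VASI75/90 will be defined with the same pattern". T-VASI50 is not named, although SAP 7.5.1.2 tabulates it.

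**The same flags elsewhere.** SAP 7.4, for the key secondary endpoint, codes F-VASI90 as 1 at ≥ 90% and 0 at < 90%, with no overlap. The SAP abbreviation list defines F-VASI50/75/90 as improvement of at least 50, 75 or 90%.

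**Relapse.** SAP Section 1 says "any participant in Cohort A who experiences relapse (defined as \leq F-VASI75) will receive ruxolitinib cream 1.5% BID". SAP 7.3 says "The primary endpoint is time to relapse (defined as < F-VASI75) for participants who are randomized in Cohort A". SAP Table 1, Section 3, the rescue footnote to Figure 1, 5.3.3 and 7.3.1 also use the strict inequality, as do protocol Sections 1, 2.2.1, 3, 4.1 and 6.7.

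**The scale.** Depigmentation is "estimated to the nearest of the following percentages: 0, 10%, 25%, 50%, 75%, 90%, or 100"% (SAP 7.2.2), and body surface area is recorded to the nearest 0.1% (SAP 7.2.1).

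**The concern.** On a finely graded score, the choice between ≤ and < would be cosmetic. F-VASI is the sum over facial sites of area times one of seven grades, and three of those grades are the complements of the three cut-offs. A value exactly on a cut-off is therefore a natural outcome of the instrument.

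If 7.2.2 is programmed as written, the code given to a tie depends on which condition runs last, and two programmers could produce different responder tables from the same data. For relapse, a reader who takes the definition from SAP Section 1 counts exactly 75% as an event, and a reader who takes it from SAP 7.3.1 does not. The protocol's own coding sentence in Section 10.4.1 does not help: it assigns the relapse code 1 to values of 75% or more and 0 to values below 50%, which does not match the relapse definition a few lines above it.

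**Working it through.** The plan gives no figure to reproduce on this point. The check applies the written inequalities to values that the scale can produce.

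**Inputs.** Grades 0, 10, 25, 50, 75, 90 and 100% (SAP 7.2.2); area in 0.1% BSA steps (SAP 7.2.1); parent-study entry at ≥ 0.5% facial BSA and F-VASI ≥ 0.5 (SAP Section 3).

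**Step 1: can ties occur?** Improvement = 100 × (B − R)/B, where B is baseline and R is current F-VASI. For one site with unchanged area, the area cancels:

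- 100% to 50%: 100 × (100 − 50)/100 = 50
- 100% to 25%: 100 × (100 − 25)/100 = 75
- 100% to 10%: 100 × (100 − 10)/100 = 90
- 50% to 25%: 100 × (50 − 25)/50 = 50

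From a baseline grade of 100%, 3 of the 7 grades fall on a cut-off.

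**Step 2: what code does a tie get?**

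| Improvement | SAP 7.2.2 rule for 1 | SAP 7.2.2 rule for 0 | SAP 7.4 | Relapse, SAP Section 1 | Relapse, SAP 7.3.1 |
|---|---|---|---|---|---|
| exactly 50% | true | true | – | yes | yes |
| exactly 75% | true | true | – | yes | no |
| exactly 90% | true | true | 1 only | no | no |

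Example: one site of 0.7% BSA at grade 100% has B = 0.70. Regraded 10%, R = 0.07 and improvement is exactly 90%, so the participant meets the Cohort A criterion, yet 7.2.2 allows F-VASI90 = 0. One grade worse, 25%, gives R = 0.175 and exactly 75%, where SAP Section 1 and SAP 7.3.1 disagree.

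**Step 3: how often?** The documents give neither the number of facial sites nor the grade distribution. Counting every attainable combination once gives shares of combinations, not of patients:

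| Setting (assumed) | exactly 50% | exactly 75% | exactly 90% |
|---|---|---|---|
| 1 site, baseline 100%, area fixed | 14.3% | 14.3% | 14.3% |
| 2 sites, baseline 100%, area fixed | 3.1% | 2.6% | 2.2% |
| 2 sites, baseline 75-100%, area fixed | 0.9% | 0.6% | 0.4% |
| 1 site, baseline 100%, area also changing | 1.5% | 1.6% | 1.4% |

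Drawing grades at random or weighting them towards good response, instead of counting them equally, gave about 9-29% for one fixed-area site and 0.7-7% for two or three sites. With changing area, one set of assumptions gave at most 2.5% and another about 1-8%. No count was made for T-VASI.

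**Step 4: arithmetic precision.** One site, baseline grade 100%, the 26 areas from 0.5 to 3.0%, in double precision. The number of exact ties that evaluate below the cut-off:

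| Formula | at 75% | at 90% |
|---|---|---|
| (B − R)/B × 100 | 4 of 26 | 4 of 26 |
| 100 × (B − R)/B | 5 of 26 | 0 of 26 |
| (1 − R/B) × 100 | 0 of 26 | 0 of 26 |

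With the first formula, 0.7% BSA at residual 25% returns 74.99999999999999, and 0.8% BSA at residual 10% returns 89.99999999999999. Under the strict rules of SAP 7.3.1 and 7.4, these would be a false relapse and a false loss of response.

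**The case against.** A reader might infer that the overlap decides who enters Cohort A, who relapses and who loses F-VASI90. The documents do not support that. Cohort A entry is ≥ F-VASI90 throughout, and participants are assigned at enrollment through the IRT, not by a derived flag in a SAP dated 06 OCT 2022. The primary analysis (SAP 7.3.1) and the key secondary (SAP 7.4) carry their own definitions without overlap. SAP Section 1 is introductory, and SAP Section 3 repeats its sentence with <. What remains is the by-visit proportions of SAP 7.5.1.2, which are descriptive; protocol 10.3 plans no formal test for them. Even there, the abbreviation list makes a value on the cut-off a response, so the intent can be recovered. All of this stands.

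A reader might also infer that a large share of readings is affected. That holds only for one patch of constant area, or for sites that move together. BSA is re-estimated at each visit, and the tie rate falls quickly with several sites or changing area.

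The precision problem depends on the formula, and the documents contain no code. That also stands, but the SAP states neither formula nor rounding, so the risk is open.

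Finally, both ≤ signs could be errors in reading the PDF. This is possible but unproven: the same reading shows < correctly beside ≥ in SAP 7.4.

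**Conclusion.** The point holds as a matter of consistency and specification. SAP 7.2.2 gives two codes to a value on the cut-off and contradicts SAP 7.4 and the abbreviation list. SAP Section 1 contradicts every other SAP statement of relapse and the protocol's endpoint, design and rescue texts. The direct effect is confined to the descriptive by-visit responder tables for F-VASI50/75/90 and T-VASI75/90. The primary and key secondary endpoints are exposed only if a programmer takes relapse from Section 1, or uses a formula that drops exact ties below the cut-off.

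The size cannot be fixed from the documents. It runs from below 1% of readings to about 25-29%, depending on assumed numbers of sites, grade distributions and stability of area, with the upper end specific to one fixed-area site. The conclusion also assumes that both ≤ symbols stand in the source PDF.

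**What to change.** 1. Check both ≤ symbols, in SAP Section 1 and SAP 7.2.2, against the source PDF. If they are reading errors, only the T-VASI50 and rounding changes below remain.
2. In SAP 7.2.2, code 0 only for improvement below the cut-off, and name all six flags, F-VASI50/75/90 and T-VASI50/75/90. This agrees with SAP 7.4 and the abbreviation list.
3. Reconcile the relapse definition in SAP Section 1 with SAP 7.3 and the protocol. Because that sentence also describes when rescue treatment is given, the medical team should confirm the single text.
4. Add one sentence: percentage improvement is rounded to a stated precision (or compared in integer units) before any cut-off is applied, for the responder flags, relapse and loss of F-VASI90 alike.

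The cost is two symbols, one flag name and one sentence in the SAP, and about one line of code. No data collection changes.

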7.2.5. Patient-Reported Outcomes

Patient-reported outcomes and quality of life will be assessed using the following tools:

• VNS (see Section 7.2.5.1)

• DLQI or CDLQI (see Section 7.2.5.5)

7.2.5.1. Vitiligo Noticeability Scale

The VNS is a patient-reported measure of vitiligo treatment success, which has a 5-point scale (Batchelor et al 2016). The baseline facial photograph from the parent study (INCB 18424-306 or INCB 18424-307) will be shown to the participants for reference and a mirror will be provided for the participants to assess the vitiligo on their face. The participant will be asked to respond to the following query:

Compared with before treatment, how noticeable is the vitiligo now? Responses: (1) More noticeable, (2) As noticeable, (3) Slightly less noticeable, (4) A lot less noticeable, and (5) No longer noticeable

VNS scores of 4 or 5 can be interpreted as representing treatment success.

7.2.5.5. Dermatology Life Quality Index

The DLQI is a simple, 10-question validated questionnaire to measure how much the skin problem has affected the participant over the previous 7 days (Finlay and Khan 1994). Participants aged \geq 16 years will answer the questionnaire with (1) very much, (2) a lot, (3) a little, or (4) not at all.

The questionnaire is analyzed under 6 headings as follows:

- Symptoms and feelings (Questions 1 and 2)
- Daily activities (Questions 3 and 4)
- Leisure (Questions 5 and 6)
- Work and school (Question 7)

- Personal relations (Questions 8 and 9)
- Treatment (Question 10)

The scoring of each question is as follows: Very much = 3; A lot = 2; A little = 1; Not at all = 0; Not relevant = 0; Question 7, "Prevented work or studying" = 3.

The following imputations will be applied for incorrectly completed questionnaires:

- If 1 question is left unanswered, this is scored 0 and the scores are summed and expressed as usual out of a maximum of 30.
- If 2 or more questions are left unanswered, the questionnaire is not scored.
- If Question 7 is answered "yes," this is scored 3. If Question 7 is answered "no," but then either "a lot" or "a little" is ticked, this is then scored 2 or 1. If "Not relevant" is ticked, the score for Question 7 is 0. If it is answered "no," but the second half is left incomplete, the score will remain 0.
- If 2 or more response options are ticked, the response option with the highest score should be recorded.
- If there is a response between 2 tick boxes, the lower of the 2 score options should be recorded.
- For the 6 DLQI subscales, if the answer to 1 question in a subscale is missing, that subscale should not be scored.

The DLQI is calculated by summing the score of each question, resulting in a maximum of 30 and a minimum of 0. The higher the score, the more quality of life is impaired.

The meaning of total DLQI scores can be categorized as follows:

- 0 to 1 =No effect
- 2 to 5 = Small effect
- 6 to 10 = Moderate effect
- 11 to 20 = Very large effect
- 21 to 30 = Extremely large effect

A change from baseline in DLQI and CDLQI score of at least 4 points is considered clinically important (Basra et al 2015, Waters et al 2010).

The questionnaire is also analyzed under 6 subscales as follows:

- Symptoms and feelings (Questions 1 and 2)
- Daily activities (Questions 3 and 4)
- Leisure (Questions 5 and 6)
- Work and school (Question 7)
- Personal relations (Questions 8 and 9)
- Treatment (Question 10)

The CDLQI is the youth/children's version of the DLQI. For participants who are aged < 16 years at baseline (Day 1) of the parent study (INCB 18424-306 or INCB 18424-307), the CDLQI will be completed instead of the DLQI throughout their participation in this extension study.

The scoring of each question is as follows: Very much = 3; Quite a lot = 2; Only a little = 1; Not at all = 0; Question unanswered = 0; Question 7: "Prevented school" = 3.

The CDLQI is calculated by summing the score of each question, resulting in a maximum of 30 and a minimum of 0. The higher the score, the more quality of life is impaired.

The questionnaire is also analyzed under 6 subscales as follows:

- Symptoms and feelings (Questions 1 and 2)
- Leisure (Questions 4, 5, and 6)
- School or holidays (Question 7)
- Personal relationships (Questions 3 and 8)
- Sleep (Question 9)
- Treatment (Question 10)

The severity banding for CDLQI scores is as follows:

- 0 to 1 = No effect on child's life
- 2 to 6 = Small effect
- 7 to 12 = Moderate effect
- 13 to 18 = Very large effect
- 19 to 30 = Extremely large effect

The following imputations will be applied for incorrectly completed questionnaires:

- If 1 question is left unanswered, this is scored 0, and the scores are summed and expressed as usual out of a maximum of 30.
- If 2 or more questions are left unanswered, the questionnaire is not scored.
- If both parts of Question 7 are completed, the higher of the 2 scores should be counted.

7.3. Analysis of the Primary Efficacy Parameter

The primary endpoint is time to relapse (defined as < F-VASI75) for participants who are randomized in Cohort A.

7.3.1. Primary Efficacy Analysis

The primary analysis will be based on the ITT-Ext population (defined as achieving ≥ F-VASI90 at Week 52). Relapse, a binary variable event, is defined as a loss of F-VASI75 response assessed as percentage improvement from baseline (Day 1 of the parent study) to F-VASI < 75%. The time to relapse is defined as the number of days from the Week 52 randomization date to the first evaluation date at which the participant meets the definition of relapse. For participants who discontinue early, complete the study without meeting criteria for the event, or received open-label rescue treatment (1.5% BID) without meeting the criteria for the event, the time to event will be censored at the last assessment date or the date of rescue treatment. Details of the censoring and missing data handling are provided in Table 2. The time-to-event data will be assessed using the Kaplan-Meier product limit method. Treatment comparisons between ruxolitinib 1.5% cream BID and vehicle cream BID will be performed using the log-rank test. Hazard ratios and the corresponding 95% CIs will be estimated using the Cox proportional hazards model. This model will include the treatment group (1.5% BID and vehicle) and stratification factors (skin type and region).

The incidence of relapse will be summarized by ruxolitinib cream 1.5% BID and vehicle at each timepoint. Swimmer plots will be provided for the time to relapse and subgroup swimmer plots by baseline characteristics, such as age group and duration of disease, will be provided.

7.4. Analysis of the Key Secondary Efficacy Parameters

The key secondary endpoint will be analyzed using the ITT-Ext population.

The key secondary endpoint will be the time to maintain \geq F-VASI90 response. For F-VASI90 response, a categorical variable event is defined to be equal to 1 (Yes) when the improvement from baseline in F-VASI is \geq 90% and 0 (No) if < 90%. The time to maintain \geq F-VASI90 response is defined as the number of days from the Week 52 randomization to the first evaluation date at which the participant has percentage change from baseline in F-VASI < 90%.

The statistical comparisons and censoring and missing data handling for the key secondary endpoint will be analyzed using a similar method as specified in the primary analysis.

7.5. Analysis of Other Secondary Efficacy Parameters

7.5.1. Other Secondary Efficacy Analysis

All other secondary efficacy analyses will be conducted based on the FAS for Cohorts A and B separately. For Cohort A, only assessments on or before the first dose date of open-label rescue treatment will be summarized and all assessments will be listed.

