6.7. Rescue Treatment

For participants in Cohort A, if there is a loss of clinically meaningful response on the face (ie, < F-VASI75) at any time, the participants will receive open-label ruxolitinib cream 1.5% BID until completing the study (ie, Week 104 or EOT).

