3.2. Control of Type I Error

All statistical analyses are exploratory in nature. No alpha control will be implemented. Unless otherwise specified, all CIs provided will be at the 95% confidence level.

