4.1.4. Handling of Missing and Incomplete Data

For the primary and key secondary endpoints, which are durations of responses, the algorithm in Table 2 will be applied to determine censoring or event.

Table 2: Algorithm for Censoring

| Situation | Date of Relapse/Lost Response or Censoring | Outcome |
|---|---|------------------------|
| Relapse/lost response documented on or between scheduled visits | Date of relapse/lost response | Relapsed/lost response |
| No relapse/maintain response | Date of last assessment | Censored |
| Treatment discontinuation | Date of last assessment | Censored |
| Applying rescue treatment (1.5% BID) in extension treatment period without relapse/lost response status | Date of rescue treatment | Censored |

For all other endpoints, no imputation will be performed for missing values unless otherwise specified.

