5.2. Treatment Groups

This is a double-blind, vehicle-controlled, randomized withdrawal and treatment extension study that will enroll eligible participants who have completed either Study INCB 18424-306 or Study INCB 18424-307 (parent studies). Data will be summarized based on the treatment regimen that was assigned at Week 52 (ITT-Ext) or that the participant actually applied (FAS).

For Cohort A, treatment groups are ruxolitinib cream 1.5% BID and vehicle cream for participants before open-label rescue treatment. For participants who cross over from vehicle cream to open-label ruxolitinib cream, the treatment group will be Vehicle-1.5% BID. For Cohort B, the treatment group will be based on the treatment assignment at Day 1 of the parent study (vehicle to 1.5% BID and 1.5% BID to 1.5% BID).

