7.5.1.2. Categorical Efficacy Endpoints

For the following categorical parameters, summary statistics, including sample size, frequency, and percentages, will be presented by visit for both cohorts.

- Proportion of participants achieving F-VASI50/75/90
- Proportion of participants achieving T-VASI50/75/90
- Proportion of participants achieving a VNS of "4 A lot less noticeable" or "5 No longer noticeable"

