APPENDIX A. PLANNED TABLES AND FIGURES

This appendix provides a list of the planned tables, figures, and listings for the CSR. Shells are provided in a separate document for tables that are not in the Standard Safety Tables v1.12.

The lists of tables, figures, listings are to be used as guidelines. Modifications of the lists that do not otherwise affect the nature of the analysis will not warrant an amendment to the SAP.

For tables and figures using the FAS population, separate tables and figures will be provided for Cohort A and Cohort B.

Tables

| Table No. | Title | Population | Standard |
|--------------|---|------------|----------|
| 1.1.1 | Analysis Populations | All | X |
| 1.1.2.1 | Summary of Participant Disposition | FAS | X |
| 1.1.3 | Summary of Number of Participants Enrolled by Country and Site | FAS | X |
| 1.1.4 | Summary of Protocol Deviations | FAS | X |
| 1.2 | Summary of Demographics and Baseline Characteristics | FAS | X |
| 1.3 | Summary of Baseline Disease Characteristics | FAS | X |
| 1.4.1 | Summary of Prior Therapy for Vitiligo | FAS | X |
| 1.4.2 | Summary of Prior Medications | FAS | X |
| 1.4.3 | Summary of Concomitant Medications | FAS | X |
| 1.5 | Summary of General Medical History | FAS | X |
| 1.6 | Summary of Participants With Assessments Not Done Due to COVID-19 Pandemic | FAS | |
| 2.1.1.1 | Summary and Analysis of Time to Relapse | ITT-Ext | X |
| 2.1.1.2 | Summary of Relapse by Visit | ITT-Ext | X |
| 2.2.1.1 | Summary and Analysis of Time to Maintain ≥ F-VASI90 | ITT-Ext | |
| 2.2.1.2 | Summary of Time to Loss of F-VASI90 Response | ITT-Ext | |
| 2.3.1.1 | Summary and Analysis of Participants Achieving F-VASI50 | FAS | X |
| 2.3.1.2 | Summary and Analysis of Participants Achieving F-VASI75 | FAS | X |
| 2.3.1.3 | Summary and Analysis of Participants Achieving F-VASI90 | FAS | X |
| 2.3.1.4 | Summary and Analysis of F-VASI | FAS | X |
| 2.3.1.5 | Shift Summary of F-VASI | FASa | |
| 2.3.2.1 | Summary and Analysis of Participants Achieving T-VASI50 | FAS | X |
| 2.3.2.2 | Summary and Analysis of Participants Achieving T-VASI75 | FAS | X |
| 2.3.2.3 | Summary and Analysis of Participants Achieving T-VASI90 | FAS | X |
| 2.3.2.4 | Summary and Analysis of T-VASI | FAS | X |
| 2.3.2.5 | Shift Summary of T-VASI | FASa | |
| 2.4.1 | Summary and Analysis of F-BSA | FAS | X |
| 2.4.2 | Summary and Analysis of T-BSA | FAS | X |
| 2.4.1 | Summary and Analysis of Participants Achieving VNS Scores of 4 or 5 | FAS | X |

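### Cohort A by-visit F-VASI75/90 summaries stop at rescue with no stated denominator; on the likely observed-case reading they exceed the share of the arm in response without rescue

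*SAP*

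**What the plan says.** - **Trigger.** Under Protocol 6.7, a Cohort A participant who falls below F-VASI75 at any time is rescued: "the participants will receive open-label ruxolitinib cream 1.5% BID until completing the study".
- **Cut at rescue.** SAP 7.5.1 bases the other secondary efficacy analyses on the FAS, by cohort, and adds: "For Cohort A, only assessments on or before the first dose date of open-label rescue treatment will be summarized". Later assessments are listed only.
- **Display.** For F-VASI50/75/90, T-VASI50/75/90 and VNS, SAP 7.5.1.2 says that "summary statistics, including sample size, frequency, and percentages, will be presented by visit for both cohorts". It names no denominator and no rule for rescued participants.
- **Missing data.** SAP 4.1.4: "For all other endpoints, no imputation will be performed for missing values unless otherwise specified".
- **Grouping.** SAP 5.2 summarises FAS data by the treatment actually applied and defines the Cohort A groups as those before rescue. It then says: "For participants who cross over from vehicle cream to open-label ruxolitinib cream, the treatment group will be Vehicle-1.5% BID".
- **Endpoint.** Protocol Table 4 and SAP Table 1 list the proportion achieving F-VASI50/75/90 during the extension period, with no restriction to unrescued participants.
- **Related output.** SAP 7.3.1: "The incidence of relapse will be summarized by ruxolitinib cream 1.5% BID and vehicle at each timepoint". Appendix A lists this as Table 2.1.1.2, "Summary of Relapse by Visit", on ITT-Ext.

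**The concern.** The cut depends on the outcome being tabulated, because participants leave the F-VASI75 summary for having lost F-VASI75. The words on or before keep the assessment that showed the relapse, so it can count once as non-response. After that the participant is in neither numerator nor denominator. A relapse found at an unscheduled visit and rescued there may never enter a scheduled-visit percentage.

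The by-visit F-VASI75 figure then tracks one minus the relapse risk since the previous visit, not the share of the arm still in response. F-VASI90 loses the same participants from its denominator. A reader could take a high, nearly flat line as durable response in the arm and could underestimate the difference between arms. Two programmers could also follow this text and produce materially different tables for a stated secondary endpoint.

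**Working it through.** The documents give no relapse rate and no power calculation, so there is no figure of the plan's own to reproduce. All relapse rates below are assumptions.

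**Inputs.** Protocol Table 3 schedules F-VASI at Weeks 56, 60, 64, 68, 80, 92 and 104, that is 4, 8, 12, 16, 28, 40 and 52 weeks after randomisation. Assumed: constant hazard, no dropout, relapse found at scheduled visits and rescued at once.

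**Formulas.** With cumulative relapse F by Week 104, S(t) = (1 − F)^(t/52).
- Observed-case F-VASI75 at Week 104 = S(52)/S(40).
- Share of the arm in response without rescue = S(52) = 1 − F.
- F-VASI90 is multiplied by 1/S(40).

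| Assumed relapse | S(40) | Observed-case | Response without rescue | Excess (points) | F-VASI90 multiplier |
|---|---|---|---|---|---|
| 5% | 0.961 | 98.8% | 95% | 3.8 | 1.04 |
| 15% | 0.882 | 96.3% | 85% | 11.3 | 1.13 |
| 30% | 0.760 | 92.1% | 70% | 22.1 | 1.32 |
| 60% | 0.494 | 80.9% | 40% | 40.9 | 2.02 |

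Example at 30%: 0.700/0.760 = 92.1%.

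**Difference between arms at Week 104.** With 30% against 15% relapse, 15 points becomes 96.3 − 92.1 = 4.2. With 60% against 15%, 45 points becomes 96.3 − 80.9 = 15.4.

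**Shape of the hazard.** With a Weibull shape of 0.7 to 1.5, the excess is 3.3 to 4.1 points at 5% relapse, 9.8 to 12.3 at 15%, 19.0 to 24.2 at 30% and 34.2 to 45.8 at 60%.

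**Departures from prompt rescue at scheduled visits.** Observed-case value at 15/30/60% relapse:
- 20% of relapsed participants not rescued and still below F-VASI75, S(52)/(S(40) + 0.2(1 − S(40))): 93.8/86.6/67.2%.
- Half without a Week 92 VASI (Protocol Appendix D allows remote visits but no remote physician efficacy assessment), S(52)/(0.5·S(40) + 0.5·S(28)): 94.5/88.3/72.4%.
- Half of last-interval relapses rescued at unscheduled visits, s/(1 − 0.5(1 − s)) with s = S(52)/S(40): 98.1/95.9/89.5%.

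Every case stays above 85/70/40%.

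**Against a summary that credits regained response.** The excess vanishes only if a share (S(52)/S(40) − S(52))/F of all relapsed participants is back at F-VASI75 at Week 104. That is 75.5% at 15% relapse, 73.7% at 30% and 68.2% at 60%.

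**The case against.** **The plan does describe a pre-rescue summary.** SAP 5.2 defines the Cohort A groups as before rescue and SAP 7.5.1 states the cut. A pre-rescue summary is a legitimate quantity, and the sample size required at each visit would show the shrinking n. This stands. It does not tell the reader that the n shrinks because of the outcome, and no title or count of rescued participants is required.

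**The observed-case reading is not certain.** The analyses are based on the FAS, so a full-FAS denominator is possible, and with rescued participants counted as non-responders it would remove the excess. The display shells are in a separate document. This also stands. The cut together with the no-imputation rule makes observed-case the likelier reading, but does not settle it.

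**A reader might take 85, 70 or 40% as actual F-VASI75 status at Week 104.** The documents do not support that. Rescued participants may regain response, the Relapse Evaluable Set (RES) curves exist to show it, and the endpoint wording does not call regained response a failure. Those figures are the share in response without rescue. Against a summary crediting regained response, the excess would be smaller.

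**A reader might infer that the trial's main result is affected, or that the treatment benefit is inflated.** Neither follows. SAP 3.2 says: "All statistical analyses are exploratory in nature". The Kaplan-Meier time to relapse, the time to loss of F-VASI90, relapse by visit and the RES curves do not use this cut, and all assessments are listed. If vehicle relapses more, the table understates the benefit of continued treatment.

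**The information is largely available elsewhere.** For F-VASI75 this is mostly true. But relapse by visit and F-VASI75 by visit could appear to disagree with nothing in the plan to explain it, and relapse by visit does not show the F-VASI90 share.

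**Conclusion.** The point holds as a minor one; the change is a cheap improvement. The cut at rescue and the absence of a denominator are in the text. On the likely observed-case reading, the Cohort A F-VASI75/90 percentages are conditional on not yet being rescued. They exceed the share of the arm in response without rescue and compress the difference between arms. The direction follows from the rescue trigger. The size cannot be known from the documents: it runs from 3.8 points at 5% assumed relapse to 40.9 at 60% under the base assumptions. If regained response is credited, the excess is smaller and disappears only if roughly two thirds to three quarters of relapsed participants are back at F-VASI75 at Week 104 (constant hazard).

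**What to change.** In SAP 7.5.1.2, for Cohort A F-VASI75 and F-VASI90:

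1. Add a by-visit summary of *response without rescue* by randomised arm. The denominator is FAS participants with an F-VASI assessment at that visit, before or after rescue. Assessments after the first rescue dose count as non-response.
2. State that this is an explicit exception to the as-applied grouping in SAP 5.2, so rescued vehicle participants stay in the vehicle arm for this table.
3. Keep the pre-rescue summaries for all endpoints, titled *among participants not yet rescued*, with a row giving the number already rescued at each visit.
4. Note that F-VASI50 stays on the pre-rescue basis and is not directly comparable with the new rows.

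**Cost.** SAP wording, one derivation for two endpoints, a title and a count row. No new data are needed: F-VASI is scheduled at every visit after enrolment, and post-rescue assessments are already listed.

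**Downsides.** Displayed percentages will be lower. Response regained after rescue is not credited in this table, including in the ruxolitinib arm, where rescue is the same cream; it stays in the RES curves and listings. The new denominator is also sensitive to missed visits. With missing shares mu (unrescued) and mr (rescued), the table shows S(52)(1 − mu)/[S(40)(1 − mu) + (1 − S(40))(1 − mr)]. At 15/30/60% relapse:
- Equal shares of 20%: 85/70/40%, no shift.
- mu = 20%, mr = 10%: 83.8/68.0/37.6%.
- mu = 10%, mr = 20%: 86.1/71.9/42.4%.

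A 10-percentage-point difference in missed visits therefore shifts the figure by about 1 to 2.5 points.
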